9.5.3. Provision of follow-up information

Following reporting of an SAE for a participant, the participants should be followed up until resolution or stabilisation of the event. Follow-up information should ideally be provided on a new SAE Form, using the SAE reference number provided by the BCTU trials team. Once the SAE has been resolved, all follow-up information has been received and the paperwork is complete, the original SAE form that was completed at site must be returned to the BCTU trials office and a copy kept in the Site File.

9.6. Reporting Procedure

On receipt of an SAE form from the site, the BCTU trials team will allocate each SAE form with a unique reference number and enter this onto the SAE form. The SAE form (containing the unique reference number completed) will be forwarded to the site as proof of receipt within 1 working day of receipt. The SAE reference number will be quoted on all correspondence and follow-up reports regarding the SAE and filed with the SAE in the TMF.

On receipt of an SAE Form, the Chief Investigator (CI) or their delegate will independently determine the seriousness and causality of the SAE. An SAE judged by the PI, the CI or their delegate to have a reasonable causal relationship with the intervention will be regarded as a related SAE. The causality assessment given by the PI will not be downgraded by the CI or their delegates. If the CI or their delegates disagrees with the PI's causality

assessment, the opinion of both parties will be documented, and where the event requires further reporting, both opinions will be provided with the report.

The CI or their delegates will also assess all related SAEs for expectedness. If the event is unexpected (i.e. is not defined in the protocol as an expected event) it will be classified as an unexpected and related SAE.

9.7. Reporting to the Research Ethics Committee

9.7.1. Unexpected and Related Serious Adverse Events

BCTU will report all events categorised as Unexpected and Related SAEs to the main Research Ethics Committee (REC) and the University of Birmingham's Research Governance Team (RGT) within 15 days.

9.7.2. Other safety issues identified during the course of the trial

The main REC and RGT will be notified immediately if a significant safety issue is identified during the course of the trial.

9.8. Investigators non-CTIMPs

Details of all Unexpected and Related SAEs and any other safety issue which arises during the course of the trial will be reported to PI. A copy of any such correspondence should be filed in the site file and TMF.

9.9. Data Monitoring Committee non-CTIMPs

The independent Data Monitoring Committee (DMC) will review all SAEs.

10. DATA HANDLING AND RECORD KEEPING

10.1. Source Data

Source data is defined as all information in original records and certified copies of original records of clinical findings, observations, or other activities in a clinical trial necessary for the reconstruction and evaluation of the trial. In order to allow for the accurate reconstruction of the trial and clinical management of the subject, source data will be accessible and maintained. Illustrative examples of source data are provided on the next page:

Data	Source
Participant Reported Outcomes	The original participant-completed CRF is the source and will be kept with the participant's trial record at site, whilst copies will be provided to the Trials Office
Lab results	The original lab report (which may be electronic) is the source data and will be kept and maintained in line with normal local practice. Information will be transcribed onto CRFs
Imaging	The source is the original imaging usually as an electronic file. Data may be supplied to the Trials Office as a password-protected, anonymised, copy of the electronic file, or as an interpretation of the imaging provided on a CRF. This will be transferred via fax or secure email, and stored on a secure computer server at the University of Birmingham. Where data is interpreted, the CRF onto which it is transcribed becomes the source. A copy of the CRF should be provided to the Trials Office.
Clinical event data	The original clinical annotation is the source data. This may be found on clinical correspondence, or electronic or paper participant records. Clinical events reported by the participant, either in or out of clinic (e.g. phone calls), must be documented in the source data.
Health Economics data	Often obtained by interview directly with the participant for transcription onto the CRF.
Recruitment	The original record of the randomisation is the source. It is held on University of Birmingham servers as part of the randomisation and data entry system.
Drop out	Where a participant expresses a wish to withdraw, the conversation must be recorded in the source data.

Source data will comprise of the hospital notes / electronic patient records, case report forms (e.g. surgical details and complications) and administered participant questionnaires to capture recovery and quality of life outcomes. Hospital source data is kept as part of the participants' medical notes generated and maintained at site.

10.2. Case Report Form (CRF) Completion

A CRF is required and should be completed for each individual participant. For the LAVA trial this will be in the form of a paper and / or electronic CRFs. The data held on the completed original CRFs are the sole property of the respective PIs whilst the data set as a whole is the property of the Sponsor and should not be made available in any form to third parties except for authorised representatives or appropriate regulatory authorities without written permission from the sponsor. Appropriate data sharing requests will be considered by the trial management group and the BCTU data sharing committee.

Data reported on each form will be consistent with the source data and any discrepancies will be explained. All missing and ambiguous data will be queried. Staff delegated to complete CRFs will be trained to adhere to standard formats. Protocol and GCP non-compliances should be added to a Protocol Deviation Log, held by the site, and reported to the Trials Office on discovery. In all cases it remains the responsibility of the site's PI or their delegate to ensure that the CRF has been completed correctly and that the data are accurate. This will be evidenced by the signature of the site's PI or their delegates on the CRF.

The completed originals will be submitted to the BCTU trials team and a copy filed in the Investigator Site File

10.3. Participant completed Questionnaires

Participant completed questionnaires can be completed in clinic, via post, online (including VOIP / video conferencing apps) or by telephone.

If completed in clinic, the questionnaire can be completed by the participant directly or by a member of the study team under the direction of the participant. The participant will be encouraged to answer the questions as fully as they can. A member of the study team will check the completed questionnaire and encourage the participant to complete any missed questions.

If completed via post, a paper questionnaire will be completed by the participant directly who will be asked to return it to the trials office in a pre-paid envelop. Upon receipt, a member of the study team will check the completed questionnaire and can contact the participant by telephone, post, text or email to query any missing data.

If completed on-line, an electronic version of the questionnaire will be completed by the participant directly. Upon submission, a member of the study team will check the completed questionnaire and can contact the participant by telephone, post, text or email to query any missing data.

If completed by remote video or telephone the questionnaire will be completed by a member of the study team under the direction of the participant. The participant will be encouraged to answer the questions as fully as they can. A member of the study team will check the completed questionnaire and encourage the participant to complete any missed questions.

10.4. **Data Management**

Data Protection Registration: The University of Birmingham has Data Protection Registration to cover the purposes of analysis and for the classes of data requested. The University's Data Protection Registration number is Z6195856.

Processes will be employed to facilitate the accuracy of the data included in the final report. These processes will be detailed in the trial specific data management plan. Coding and validation will be agreed between the trial's coordinator, statistician and programmer and the trial database will be signed off once the implementation of these has been assured.

Data can be entered onto the bespoke trial database by staff at BCTU, delegated staff at site or, in the case of participant completed questionnaires, the participant themselves if an on-line option is available. The data capture system will conduct automatic range checks for specific data values to ensure high levels of data quality. Queries on the trial data will be raised using the integrated data query system in the trial database, with the expectation that these queries will be completed by the site within 30 days of receipt. Overdue data queries will be requested on a monthly basis until receipt of the data or a file note to explain its absence.

10.5. **Data Security**

The security of the System is governed by the policies of the University of Birmingham. The University's Data Protection Policy and the Conditions of Use of Computing and Network Facilities set out the security arrangements under which sensitive data should be processed and stored. All studies at the University of Birmingham have to be registered with the Data Protection Officer and data held in accordance with the Data Protection Act. The University will designate a Data Protection Officer upon registration of the study. The Study Centre has arrangements in place for the secure storage and processing of the study data which comply with the University of Birmingham policies.

The System incorporates the following security countermeasures:

- Physical security measures: restricted access to the building, supervised onsite repairs and storages of back-up tapes/disks are stored in a fire-proof safe.
- Logical measures for access control and privilege management: including restricted accessibility, access controlled servers, separate storage of non-identifiable data etc.
- Network security measures: including site firewalls, antivirus software, separate secure network protected hosting etc.
- System Management: the System shall be developed by the BCTU Programming Team and will be implemented and maintained by the BCTU Programming Team.
- System Design: the system shall comprise of a database and a data entry application with firewalls, restricted access, encryption and role based security controls.
- Operational Processes: the data will be processed and stored within the Study Centre (University of Birmingham).
- Data processing: Statisticians will only have access to anonymised data.
- System Audit: The System shall benefit from the following internal/external audit arrangements:

- Internal audit of the system
- An annual IT risk assessment
- Data Protection Registration: The University of Birmingham has Data Protection Registration to cover the purposes of analysis and for the classes of data requested. The University's Data Protection Registration number is Z6195856.

10.6. Archiving

It is the responsibility of the PI to ensure all essential trial documentation and source documents (e.g. signed ICFs, Investigator Site Files, Pharmacy Files, participants' hospital notes, copies of CRFs etc.) at their site are securely retained for at least ten years.

These essential trial and source documents must not be destroyed without express, written authorisation from a senior member of the management team at Birmingham Clinical Trials Unit.

11. QUALITY CONTROL AND QUALITY ASSURANCE

11.1. Site Set-up and Initiation

The CI is required to sign a UoB CI agreement to document the expectations of both parties. The UoB CI agreement document must be completed prior to participation. The CI is required to sign a Clinical Trials Task Delegation Log which documents the agreements between the CI and BCTU.

All local PIs will be asked to sign the necessary agreements including a Site Signature and Delegation log between the PI and the CTU and supply a current CV and GCP certificate to BCTU. All members of the site research team are required to sign the Site Signature and Delegation Log, which details which tasks have been delegated to them by the PI.

Prior to commencing recruitment, each recruiting site will undergo a process of initiation, either a meeting or a teleconference, at which key members of the site research team are required to attend, covering aspects of the trial design, protocol procedures, adverse event reporting, collection and reporting of data and record keeping. Sites will be provided with an Investigator Site File containing essential documentation, instructions, and other documentation required for the conduct of the trial. The BCTU trials team must be informed immediately of any change in the site research team.

11.2. Monitoring

The monitoring requirements for this trial have been developed following trial specific risk assessment by BCTU and as documented in the monitoring plan.

11.3. Onsite Monitoring

For this trial we will monitor sites in accordance with the trial risk assessment and monitoring plan. Any monitoring activities will be reported to the trials team and any issues noted will be followed up to resolution. Additional on-site monitoring visits may be triggered, for example by poor CRF return, poor data quality, low SAE reporting rates, excessive number of participant withdrawals or deviations (also defined in the monitoring plan). Investigators will allow the LAVA trial staff access to source documents as requested. The monitoring will be conducted by BCTU.

11.4. Central Monitoring

Trials staff will be in regular contact with the site research team to check on progress and address any queries that they may have. Sites will be requested to send in copies of signed ICFs and other documentation for central review for all participants providing explicit consent. This will be detailed in the monitoring plan. Trials staff will check incoming ICFs and CRFs for compliance with the protocol, data consistency, missing data and timing. Sites will be sent DCFs requesting missing data or clarification of inconsistencies or discrepancies.

11.5. Audit and Inspection

The Investigator will permit trial-related monitoring, audits, ethical review, and regulatory inspection(s) at their site, providing direct access to source data/documents. The investigator will comply with these visits and any required follow up. Sites are also requested to notify BCTU of any relevant inspections.

11.6. Notification of Serious Breaches

The Sponsor is responsible for notifying the REC of any serious breach of the conditions and principles of GCP in connection with that trial or the protocol relating to that trial. Sites are therefore requested to notify the Trials Office of any suspected trial-related serious breach of GCP and/or the trial protocol. Where the Trials Office is investigating whether or not a serious breach has occurred sites are also requested to cooperate with the Trials Office in providing sufficient information to report the breach to the REC where required and in undertaking any corrective and/or preventive action.

Sites may be suspended from further recruitment in the event of serious and persistent non-compliance with the protocol and/or GCP, and/or poor recruitment. Any major problems identified during monitoring may be reported to the LAVA management and oversight committees and the REC. This includes reporting serious breaches of GCP and/or the trial protocol to the REC and MHRA.

A copy of the notification will be sent to the University of Birmingham Clinical Research Compliance Team at the time of reporting to the REC.

12. END OF TRIAL DEFINITION

The end of trial will be 9 months after the last data capture. This will allow sufficient time for the completion of protocol procedures, data collection and data input. The Trials Office will

notify the REC that the trial has ended within 90 days of the end of trial. Where the trial has terminated early, the Trials Office will inform the REC within 15 days of the end of trial. The Trials Office will provide them with a summary of the clinical trial report within 12 months of the end of trial.

A copy of the end of trial notification as well as the summary report will also sent to the University of Birmingham Research Governance Team. At the same time these will be sent to the REC.

The BCTU trial team will notify the main REC and University of Birmingham Research Governance Team that the trial has ended within 90 days of the end of trial and will provide them with a summary of the clinical trial report within 12 months of the end of trial.

13. STATISTICAL CONSIDERATIONS

13.1. Sample Size

To enable 90% power to test the non-inferiority hypothesis at a one-sided 2.5% significance level (two-sided 5% level) assuming a 3% margin of non-inferiority and a major surgical complication rate of 6% in the abdominal (control) group requires 2634 participants. The estimate of 6% is taken from a similar previous comparative study.¹¹ A 3% margin is justifiable because of the trade-off of potentially swifter recovery with laparoscopic surgery; a view shared by our patient focus group and is substantially less than the 5% difference observed in the previous major trial,¹¹ which led to the continued use of open abdominal hysterectomy.

An extra consideration is the potential for clustering by surgeon due to the expertise based design.^{19 34} Under the assumption that each of the 50 centres will utilise 6 surgeons (operating on approximately 9 patients on average during the study), along with an intra-cluster correlation (ICC) estimate of 0.02, the sample size has been increased by 16% to 3055. This ICC estimate used - in the absence of precise estimates - is considered conservative given the outcome is clinical and of low prevalence, both of which are factors associated with low ICC.^{35, 36} However, even varying these factors up to an ICC of 0.07 or average cluster size of 29, shows we will have at least 80% power to establish non-inferiority in these situations.

A final inflation of 6% to account for loss to follow-up (similar to the aforementioned previous study) brings the final sample size total to 3250 participants. This size of sample would give the ability to detect meaningful differences between groups in our key secondary outcome of time from surgery to resumption of usual activities. Assuming the median recovery time in the abdominal group is between 6 and 9 weeks³⁷ we will have high levels of power (>90%) to detect reductions of 1 week in all cases.

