6.3. Randomisation

Randomisation will be provided by a secure online randomisation system at the Birmingham Clinical Trials Unit (BCTU) (available at <http://www.trials.bham.ac.uk/lava>). Unique log-in usernames and passwords will be provided to those who wish to use the online system and who have been delegated the role of randomising participants into the study as detailed on the LAVA Trial Signature and Delegation Log. The online randomisation system will be available 24 hours a day, 7 days a week, apart from short periods of scheduled maintenance. A freephone telephone randomisation service ([name]) is available Monday to Friday, 09:00 to 17:00 UK time, except for bank holidays and University of Birmingham closed days.

After participant eligibility has been confirmed and informed consent has been received, the participant can be randomised into the trial. Randomisation Notepads will be provided to investigators and may be used to collate the necessary information prior to randomisation. All questions and data items on the Randomisation Notepad must be answered before a Trial Number and allocation can be given. If data items are missing, randomisation will be suspended, but can be resumed once the information is available. Only when all eligibility criteria and baseline data items have been provided will a Trial Number be allocated.

Participants will be randomised at the level of the individual in a 1:1 ratio to undergo their hysterectomy by either a laparoscopic or open abdominal route.

A minimisation algorithm will be used within the online randomisation system to ensure balance in the treatment allocation over the following variables:

- Previous caesarean section (yes / no)
- BMI (≤ 29.9 , 30-34.9, ≥ 35 Kg/m²)
- Uterine Size (≤ 12 weeks, > 12 weeks)
- Planned retention of cervix (yes / no)
- Recruiting centre

A 'random element' will be included in the minimisation algorithm, so that each patient has a probability (unspecified here), of being randomised to the opposite treatment that they would have otherwise received. Full details of the randomisation specification will be stored in a confidential document at BCTU.

Following randomisation, a confirmatory e-mail will be sent to the randomiser, the local PI and the trial co-ordinator, with the participant's unique trial number.

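### Section 13.1 assumes about 9 women per surgeon, but its own 300 surgeons and 3055 women give about 10.2; on its own formula, power at an ICC of 0.07 is then about 78%, not at least 80%

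*Protocol*

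**What the plan says.** All the figures are in Protocol Section 13.1, Sample Size.

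- **Before clustering:** "assuming a 3% margin of non-inferiority and a major surgical complication rate of 6% in the abdominal (control) group requires 2634 participants", for 90% power at a one-sided 2.5% level.
- **Surgeons and caseload:** "Under the assumption that each of the 50 centres will utilise 6 surgeons (operating on approximately 9 patients on average during the study".
- **Inflation for clustering:** "along with an intra-cluster correlation (ICC) estimate of 0.02, the sample size has been increased by 16% to 3055".
- **Loss to follow-up:** a further 6% brings the total to 3250.
- **Robustness:** "even varying these factors up to an ICC of 0.07 or average cluster size of 29, shows we will have at least 80% power".

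The section says that no precise ICC estimates were available and describes 0.02 as conservative. Section 6.3 gives individual 1:1 allocation. Section 13.2.4 leaves women with missing primary outcome data out of the primary analysis in the first instance, so 3055 is the number planned for analysis.

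**The concern.** Three stated quantities do not fit together: 300 surgeons, about 9 women each, and 3055 women. Three hundred surgeons with 9 women each treat 2700, a number the section uses nowhere. A caseload of 10.2 does not round to 9.

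The cluster size feeds the design effect, and the design effect feeds both the sample size and the robustness sentence. That sentence carries weight, because it is how the protocol defends an ICC chosen without precise estimates. A reader judging whether surgeon variation threatens the trial will take its 80% as a floor.

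**Working it through.** **Inputs (Section 13.1 unless stated).** Control rate 6%; margin 3 percentage points; one-sided alpha 2.5%; power 90%; 1:1 allocation (Section 6.3); 50 x 6 = 300 surgeons; about 9 women each; ICC 0.02, varied to 0.07; 6% loss. The laparoscopic rate is not stated. I take it as 6% (no true difference) because that reproduces 2634 exactly.

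**Reproducing the plan**

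1. Per arm: (1.96 + 1.2816)^2 x 2 x 0.06 x 0.94 / 0.03^2 = 1317, so 2634 in total.
2. Design effect: DE = 1 + (m - 1) x ICC = 1 + 8 x 0.02 = 1.16, and 2634 x 1.16 = 3055. The stated 16% is therefore exactly m = 9.
3. Loss: 3055 / 0.94 = 3250.
4. Power: effective size ESS = N / DE; SE = sqrt(2 x 0.06 x 0.94 / (ESS/2)); power = Phi(0.03/SE - 1.96).
5. Robustness limits: m = 9 with ICC 0.07 gives DE = 1 + 8 x 0.07 = 1.56. With m = 29 and ICC 0.02, DE = 1 + 28 x 0.02 = 1.56. Both give ESS = 3055/1.56 = 1958 and power 79.8%, which is 80% to the whole percent.

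**Implied caseload**

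- 2634/300 = 8.8
- 3055/300 = 10.2
- 3250/300 = 10.8

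**Same formula, consistent caseload**

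| N | m | ICC | DE | ESS | Power |
|---|---|---|---|---|---|
| 3055 | 9 | 0.02 | 1.160 | 2634 | 90.0% |
| 3055 | 10.2 | 0.02 | 1.184 | 2581 | 89.4% |
| 3055 | 9 | 0.07 | 1.560 | 1958 | 79.8% |
| 3055 | 10.2 | 0.07 | 1.643 | 1860 | 77.8% |
| 3250 (no loss) | 10.8 | 0.07 | 1.688 | 1925 | 79.1% |

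**Where 80% is lost.** Without clustering, 80% power needs 1968 women, so the largest tolerable DE is 3055/1968 = 1.552. With m = 10.2 the ICC limit is 0.552/9.18 = 0.060. With m = 9 it is 0.552/8 = 0.069.

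**Surgeons needed for 9 each.** 3055/9 = 339, or about 340.

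**The case against.** **The plan's own figures reproduce, and 79.8% is 80%.** This stands. With 9 women per surgeon the robustness sentence is right to the precision used, and the 0.2-point gap is rounding. The point rests only on 9 not matching 300 surgeons and 3055 women.

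**The section already varies cluster size up to 29.** This also stands, and it limits the point. That scenario sets its own cluster size, so the slip does not touch it, and 10.2 lies well inside the range covered at an ICC of 0.02. It does not cover 10.2 at an ICC of 0.07.

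**Surgeons may operate in both arms.** Sections 7.1 and 8.2.1 allow this for those who meet both experience thresholds. For a surgeon balanced across arms with the same effect in each, the effect cancels from the comparison and DE is about 1 - ICC. If 13% of women had such surgeons, the average DE at ICC 0.07 would be 0.87 x 1.643 + 0.13 x 0.93 = 1.55, and power about 80%. That share is illustrative; the protocol gives none. The objection shows that 78% is conditional on nesting. It does not rescue the stated figure, because the design effect in Section 13.1 takes no credit for such surgeons.

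**Count all 3250 women.** The last 6% is there to be lost. Even with no loss, 3250 women over 300 surgeons gives 79.1%.

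**Stronger readings.** A reader might infer that the trial is underpowered and must grow. At the design ICC the loss is 0.6 of a point, so the documents do not support that. A reader might also add a penalty for unequal caseloads. They would push power down, but the protocol speaks only of an average and gives no spread, so any figure would be invented. Finally, 2634/300 = 8.8 suggests that the caseload was taken before inflation, but the section does not say how 9 was obtained.

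**Conclusion.** The point holds as a small internal inconsistency with one stated consequence that is wrong on the protocol's own inputs. About 9 women per surgeon should be about 10.2. At ICC 0.02 the design effect becomes 1.18 and power about 89.4%, which does not undermine the sample size. At ICC 0.07 power is about 78%, some two points below the claimed floor, and the floor holds only up to an ICC of about 0.06.

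These figures assume a true difference of zero, equal caseloads, 300 surgeons, 3055 women analysed and each surgeon working in one arm. The first reproduces 2634; equal caseloads and nesting within arm are implicit in the simple design effect that reproduces 3055. Surgeons working in both arms would raise power, so it would go too far to say that the trial will fall below 80% at an ICC of 0.07. What can be said is that the calculation in Section 13.1 does not deliver that floor.

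**What to change.** Keep 3250. In Section 13.1 do one of the following:

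- **Correct the caseload.** Give the average cluster size as about 10, the design effect as 1.18 and power as about 89% at ICC 0.02. Restate the robustness claim as about 78% at ICC 0.07, or as at least 80% up to an ICC of 0.06.
- **Correct the surgeon count.** If 9 women per surgeon is what was meant, give the number of surgeons that fits it (about 340 for 3055 women), and state power at ICC 0.07 as about 80% instead of as a lower bound.

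In either case, leave the scenario with 29 women per surgeon in place, described as about 80%. Add one sentence saying that the figures assume surgeons nested within arm and that surgeons operating in both arms would raise power.

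The cost is wording only. Recruitment, margin and analysis stay the same. Under the first option the stated power becomes slightly less favourable; under the second the surgeon assumption must be one the sponsor can support.
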